### 1.3 Non-Clinical and Clinical Study Findings

The same 'SPM Active' dietary supplement to be administered to obese subjects in this clinical trial was previously used as intervention in a human clinical trial by Dalli et al, and found to be safe at doses up to 4.5g in healthy individuals. The investigators concluded that SPM supplementation leads to an increase in peripheral blood SPM concentrations and reprograms peripheral blood cells, thus indicating a role for SPMs in mediating immunological activity.

### 1.4 Relevant Literature and Data

Obesity is a growing national and global epidemic. In the United States; over 35% of Americans are currently obese (Body mass index (BMI)  $\geq 30$  kg/m^2), and another one-third overweight (BMI: 25-29.9 kg/m^2). Obesity is associated with numerous chronic health conditions, including insulin resistance, type-2 diabetes, hyperlipidemia and hypertension, leading to what is termed as the metabolic syndrome. Chronic inflammation, a central component of obesity, significantly contributes to the development of these metabolic complications and has been associated with accumulation of visceral adipose tissue and immune cell infiltration. Recently, the metabolism of immune cells has emerged as a major therapeutic target for improving chronic inflammation and whole-body metabolism, as immune cells have fundamentally different metabolic programming between pro- and anti-inflammatory subsets.

Specialized pro-resolving mediators (SPMs) have recently emerged as a target for improving chronic inflammation. SPMs known as protectins, resolvins, lipoxins and maresins, are potent metabolites enzymatically synthesized from n-3 polyunsaturated fatty acids (PUFA) eicosapentaenoic (EPA) and docosahexaenoic acids (DHA). Our research, in agreement with other labs, have discovered that metabolites of the SPM family are decreased across a range of tissues in mouse models of obesity and in circulation of obese individuals. To exemplify, we have reported that the DHA-derived SPMs 14-HDHA and 17-HDHA are lowered in the spleens of obese C57BL/6J mice. We are also finding a strong reduction in the EPA-derived SPM known as 18-HEPE in white adipose tissue and liver of obese mice relative to lean controls (Fig. 1). Overall, our results are highly consistent with data from a recent study to show that 14HDHA, 17-HDHA, and 18-HEPE are lowered in circulation of obese subjects.

SPMs have insulin/glucose-normalizing properties. Rigorous literature reports demonstrate that EPA- and DHA-derived SPMs improve varying aspects of murine metabolism including insulin resistance and hepatic steatosis. We have investigated the effects of resolvin E1 (the downstream product of 18-HEPE) on hyperglycemia and hyperinsulinemia of obese male C57BL/6J mice. Administration of resolvin E1 to obese male mice at 300ng per mouse per day for 4 days prior to sacrifice has no effect on body weight (Fig. 2A) or food intake (data not shown). Resolvin E1 completely restores high fat diet-induced hyperglycemia (Fig. 2B) and strongly improves hyperinsulinemia (Fig. 2C).

## 2 STUDY OBJECTIVE

The purpose of the study is to determine the efficacy of SPM supplementation on chronic inflammation in obese human subjects. The premise is based on the notion that SPMs are lowered in obese individual. Therefore, it is hypothesized that exogenous administration of SPMs to obese individuals may have therapeutic value as insulin/glucose sensitizing agents by targeting inflammatory pathways. This application breaks new ground by taking the first steps toward translating SPMs from the pre-clinical level to obese

humans. We propose a bioavailability study in which we will establish the concentration of SPMs in plasma and PBMCs of obese subjects (primary aim) in response to dietary supplementation with SPMs. Additional exploratory measurements that correlate metabolic parameters with SPM concentration are proposed in our secondary aim.

## 2.1 Primary Objective

Our primary objective is to compare immunological fitness pre- and post- oral SPM administration in the obese:

- **Aim 1a: To quantify SPM concentrations in plasma, serum and PBMCs before and after oral SPM supplementation.** We will measure SPMs in 100µl of plasma and  $2 \times 10^6$  PBMCs. PBMCs will be isolated with established protocols in our lab. The rationale for PBMCs vs. plasma is to compare whether SPM levels in PBMCs are higher than plasma or vice versa, indicating SPM uptake into the immune cells or lack thereof. We will also measure other lipid metabolites involved in the inflammatory resolution process including thromboxanes, leukotrienes, prostaglandins, epoxy fatty acids, eoxins, mono-, di-, and tri-hydroxy fatty acids, and hepoxilins. Blinded samples will be shipped to our collaborator [name] for two-dimensional reverse phase HPLC tandem mass spectrometry.
- **Aim 1b: To measure antibody responses of B cells in PBMC pool with *in vitro* stimulation and cytokine production before and after SPM supplementation.** B cells will be directly stimulated in the PBMC isolate to mimic their natural environment. Then, antibody concentrations will be measured from the supernatants of the cultured cells via ELISA for pre- and post-intervention samples.

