### **6 STATISTICAL CONSIDERATION**

#### **6.1 Primary Endpoint**

The primary aim of the study is designed and powered to measure an increase in 18-HEPE, 17-HDHA, and 14-HDHA in Aim 1. At a family-wise error rate of 5% controlling for testing of three metabolites mentioned above,  $n=9$  will provide more than 80% power to detect a 50%-fold change increase in metabolite levels within each subject. We are assuming a similar effect size for both males and females and are doubling the sample size ( $n=18$ , 9 per sex) to allow us to subset the data in case we find divergent results between sexes. To account for possible loss-to-follow up, we increased the sample size from 18 to 24 ( $n=12$  male + 12 female). Power analysis was conducted assuming a paired t-test on pre- and post-treatment metabolite levels for three pre-specified metabolites. Expected variability of within subject differences in metabolite levels was assessed from a previous dataset and the median standard deviation was calculated across all

metabolites. Power analyses were calculated by [name] in the UNC Department of Biostatistics. Note that all analyses will be conducted in the R statistical software.

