- **Aim 1a:** SPM lipidomic measurements will be analyzed pre/post supplementation. Each SPM metabolite's distribution will be assessed for normality and homogeneity of variance using the Shapiro-Wilks test and Bartlett test respectively. However, normality will also be assessed via a qqplot of the standardized residuals and we will visualize the distribution of our data with a histogram. In addition, to corroborate the Bartlett test we will check the homogeneity of variance of the residuals (homoscedasticity) using a scale-location plot where the square roots of the absolute values of the standardized residuals are plotted. If the metabolite's distribution satisfies the assumption of normality & homogeneity of variance then a paired two-tailed Student's T-test will be used to generate p-values corresponding to differences before and after supplementation. If the assumption of homoscedasticity is not met, the data will be analyzed using a paired Welch T-test. Another alternative would be to apply a log or square root transformation. However, if the data still fails the assumptions of normality and homoscedasticity it will be analyzed with a paired Wilcoxon rank sum test. All p-values will undergo a Benjamini-Hochberg adjustment (optimal for large-scale multiple hypothesis testing) at a false discovery rate of 5% to account for multiple hypothesis testing between metabolites.
- **Aim 1b:** Antibody concentrations measured via ELISA will be tested for the assumptions of normality and homogeneity of variance using the Shapiro-Wilks test and Bartlett test respectively. However, normality will also be assessed via a qqplot of the standardized residuals and we will visualize the distribution of our data with a histogram. In addition, to corroborate the Bartlett test we will check the homogeneity of variance of the residuals (homoscedasticity) using a scale-location plot where the square root of the standardized residuals is plotted. Data that passes both assumptions will be analyzed via a paired two sample Student T-test. Data that fails the assumption of homoscedasticity will be analyzed using a paired Welch T-test. Another alternative would be to apply a log or square root transformation. However, if the data still fails the assumptions of normality and homoscedasticity it will be analyzed with a paired Wilcoxon rank sum test. All p-values from these analyses will undergo a Bonferroni p-value adjustment (optimal for smaller-scale multiple hypothesis testing).

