### **6.4 Sample Size and Power**

Experimental rigor is ensured through the analyses of blinded samples. The study is designed and powered to measure an increase in 18-HEPE, 17-HDHA, and 14-HDHA in Aim 1. Additional measures in Aim 2 are exploratory, but necessary for future grant applications to demonstrate the feasibility of the approach. At a family-wise error rate of 5% controlling for testing of three metabolites mentioned above, n=9 will provide more than 80% power to detect a 50%-fold change increase in metabolite levels within each subject. We are assuming a similar effect size for both males and females and are doubling the sample size (n=18, 9 per sex) to allow us to subset the data in case we find divergent results between sexes. To account for possible loss to follow-up, we will increase sample size from 18 to 24 (n=12 male + 12 female). Power analysis was conducted assuming a paired t-test on pre- and post-treatment metabolite levels for three pre-specified metabolites. Expected variability of within subject differences in metabolite levels was assessed from a previous dataset and the median standard deviation was calculated across all metabolites. Power analyses were calculated by [name] in the UNC Department of Biostatistics.

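### The documents give two different primary objectives, power only three metabolites, and set no single error rate across Aims 1a and 1b

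*Combined protocol and SAP*

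**What the plan says.** **What is primary.** Section 2.1 says "Our primary objective is to compare immunological fitness pre- and post- oral SPM administration in the obese", and the synopsis agrees. Both put Aim 1a (SPM concentrations in plasma, serum and PBMCs) and Aim 1b (B-cell antibody responses and cytokine production) under that objective. Section 2, directly above, describes the study differently: "We propose a bioavailability study in which we will establish the concentration of SPMs in plasma and PBMCs of obese subjects (primary aim".

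**What is powered.** Section 6.1, Primary Endpoint, opens with "The primary aim of the study is designed and powered to measure an increase in 18-HEPE, 17-HDHA, and 14-HDHA in Aim 1". Section 6.4 gives the terms: "At a family-wise error rate of 5% controlling for testing of three metabolites mentioned above, n=9 will provide more than 80% power", for a paired t-test and a 50% within-subject rise. The synopsis carries the same statement. The synopsis and Section 6.4 call only Aim 2 exploratory.

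**How error is controlled.** Section 6.1 covers both parts of Aim 1. Aim 1a gets Benjamini-Hochberg at a 5% false discovery rate across metabolites. For Aim 1b the text is "All p-values from these analyses will undergo a Bonferroni p-value adjustment (optimal for smaller-scale multiple hypothesis testing", with no level and no count of tests. The synopsis allows either method and attaches a 5% false discovery rate to the choice. Section 6.3 allows either method and gives no level.

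**The concern.** Two readings of the primary objective are open, and they lead to different claims. Under Section 2.1, a rise in circulating metabolites counts towards an objective named immunological fitness, although it shows exposure and not B-cell function. Under the same section, a result in Aim 1b alone could be presented as primary success, although nothing in the plan sizes the study for it. Under Section 2 neither would follow.

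The choice matters because Section 1.1 says the B-cell work will settle whether supplementation relieves the impaired humoral response of obese subjects. That conclusion rests on the part of Aim 1 that has no power statement. No hierarchy, alpha split or joint success rule links the two parts, so what counts as meeting the primary objective is undefined before the data are seen.

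**Working it through.** **1. The plan's own power figure.** Inputs from Section 6.4: n = 9, paired t-test, family-wise 5% over three metabolites, 50% rise, power above 80%. Section 6.1 makes the Aim 1a test two-tailed. The SD of the differences is described by its source but not given, so the figure cannot be reproduced. It can be inverted.

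- Per-test alpha, taking Bonferroni as the intended control: 0.05/3 = 0.0167, two-sided.
- Noncentral t with 8 df and noncentrality dz × √9, where dz is the mean difference divided by the SD of the differences. Power of 80% needs dz = 1.3226.
- Largest SD at which a 50% rise gives 80% power: 0.50/1.3226 = 0.378 of baseline.
- Power at n = 9 over an assumed SD range (fraction of baseline): 0.30 gives 95%, 0.35 gives 86%, 0.40 gives 75%, 0.50 gives 53%.

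The claim of more than 80% is therefore possible but cannot be checked. The enrolment step does reproduce: 18/(1 − 0.25) = 24, so 24 allows for 25% loss.

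**2. The passages side by side.**

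| Place | What is primary | Powered? |
|---|---|---|
| Synopsis objectives; Section 2.1 | Immunological fitness: Aims 1a and 1b | Three metabolites in 1a only |
| Section 2 | SPM concentration in plasma and PBMCs | Three metabolites only |
| Section 6.1 | Three metabolites in the opening text; then methods for both 1a and 1b | Three metabolites only |
| Section 6.4 | Not restated; three metabolites powered | Three metabolites only |

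Section 2 omits serum, which Section 2.1 includes. No place names one primary matrix.

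**3. Error rate across Aim 1.** When every null is true, any rejection is false, so the false discovery rate equals the family-wise rate and Benjamini-Hochberg at 5% gives about 5% for Aim 1a. Section 6.1 states no level for Aim 1b; 5% is assumed here.

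- Independent families: 1 − (1 − 0.05)² = 0.0975, or 9.75%.
- Otherwise: at most 0.05 + 0.05 = 0.10. This is approximate, because Benjamini-Hochberg guarantees 5% only for independent or positively dependent tests.

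**4. Mismatch inside Aim 1a.** The power statement assumes family-wise 5%; the analysis controls the false discovery rate. Once some effects are real, these differ. In a simulation (n = 18, independent tests, dz = 1.32 for real effects), the family-wise error of Benjamini-Hochberg at 5% was:

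| Real effects | Family-wise error |
|---|---|
| 2 of 3 | 5.1% |
| 1 of 3 | 6.5% |
| 6 of 9 | 11.3% |
| 3 of 9 | 12.5% |

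Nine tests would correspond to three metabolites in three matrices.

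**5. What Aim 1b could detect.** No power can be computed from the documents. With 18 completers and Bonferroni at an assumed 5%, the smallest standardised change detectable with 80% power is dz = 0.70, 0.79 or 0.83 for one, two or three tests. The number of tests is also an assumption.

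**The case against.** The strongest reply is that the documents already separate the two ideas and never overclaim. The synopsis rationale makes SPM concentration the first objective and attaches immune fitness to the B-cell work; Section 1.1 draws the same line. The power of more than 80% is claimed only for the three metabolites. Section 6.3 already plans estimates with confidence intervals and/or standard errors. In a single-arm convenience-sample pilot of 24, a joint alpha over two aims may look like more formality than the design calls for.

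Much of this stands, and it rules out several stronger readings that a reader might infer:

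- *Each of Aims 1a and 1b has its own 5% family-wise error.* Section 6.1 gives 1a a false discovery rate and gives 1b no level. The only 5% that could reach 1b is in the synopsis, which calls it a false discovery rate.
- *The false-positive risk is 9.75%.* That needs the assumed 5% for 1b, every null true, independent families, and a rule that success in either aim suffices. Both aims use the same subjects and blood draws, and no such rule is written.
- *A null Aim 1b could not be interpreted.* An interval can be read without prior power; it may simply be wide.
- *Section 2 already makes the three metabolites primary.* It refers to SPM concentration in plasma and PBMCs and does not name them.

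The reply does not remove the contradiction. The synopsis objectives and Section 2.1 still give the primary objective the wider name, Section 6.1 still treats Aim 1b under the primary endpoint, and no text ranks it below 1a.

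**Conclusion.** The point holds as an inconsistency over what is primary. One part of the text makes Aims 1a and 1b jointly primary under the name immunological fitness; another makes concentration alone primary; the sample size supports only three metabolites. Aim 1b is listed as primary with no effect size, SD, power or number of tests, and the primary claim has no single error rate.

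The size of the error-rate problem is conditional: 9.75%, or at most about 10%, if Aim 1b is held at 5% and every null is true. With real effects present, the false discovery rate in Aim 1a can itself exceed family-wise 5%, by an amount that depends on the number of tests.

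A reader might infer that the metabolite power is wrong. The documents do not show that: it is stated only for the metabolites and cannot be checked without the SD. For a 24-subject pilot the consequence is an undefined primary claim, not a failed confirmatory test. It should be corrected before the data are seen.

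**What to change.** 1. In the synopsis and Sections 2.1 and 6.1, make the pre/post change in 18-HEPE, 17-HDHA and 14-HDHA, in one matrix named before the data are seen, the sole primary endpoint. Bring Section 2 into line on the matrix.
2. Test those three at the family-wise 5% that the power statement assumes, for example Bonferroni or Holm over three tests. Keep Benjamini-Hochberg at 5% for the wider metabolite panel. Replace the either-method sentences in the synopsis and Section 6.3 to match.
3. Move Aim 1b to secondary, with its number of tests listed, Bonferroni at a stated 5%, and confidence intervals.
4. Use immunological fitness only for the Aim 1b result, as the synopsis rationale and Section 1.1 already do.

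This changes wording only and adds no subjects or assays. The downside is that Aim 1b can no longer carry a primary claim.

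If the sponsor prefers to keep Aim 1b primary, it needs its own power statement and a hierarchy or alpha split. With an equal split, each metabolite is tested at 0.025/3 = 0.0083. At the effect that just gives 80% under the present plan (dz = 1.32), power per metabolite at n = 9 falls from 80.0% to 67.8%, and n = 11 is needed to restore 80%. At n = 18 it is 99.1%, so the loss falls mainly on the sex-specific subsets.

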## 2.2 Secondary Objective

Our secondary objective is to compare metabolic profiles in response to an oral dose of SPMs in the obese:

- **Aim 2a: To measure fasting insulin and fasting glucose before and after intervention.** Blood samples from baseline and post-intervention will be used to measure fasting glucose (mg/dL) and fasting insulin (ng/mL) through McClendon labs. Exploratory studies will test if obese adult participants taking a daily dose of SPMs have lower mean fasting levels of serum insulin and glucose after 4 weeks of SPM administration, relative to baseline. Participants will be asked by the study coordinator about the extent to which they complied with dosing at the end of week 2 and week 3 following the start of supplementation
- **Aim 2b: To correlate pre- and post- metabolic measurements with measured pre- and post- SPM concentrations.** Anthropomorphic and blood pressure measurements will be taken. Each subject will have his/her insulin (in ng/dL) and glucose (in mg/dL) measured pre/post supplementation through Family Medicine and the [name] lab will determine SPM concentrations in the plasma pre/post supplementation. Insulin and glucose measurements will then be correlated with measured SPM levels.

## 3 INVESTIGATIONAL PLAN (brief overview)

### 3.1 Study Design

We will conduct a non-randomized uncontrolled clinical trial to measure the efficacy of SPM administration in the obese. We will selectively recruit (n=24) obese subjects (BMI 30-40 kg/m^2) and administer an SPM formulation ("SPM Active") provided by Metagenics for 4 weeks. The study design will rely on blood samples collected at baseline and at the end of the 4-week intervention. All analyses will rely on

comparisons between pre- and post-intervention. The concentration of SPMs, in addition to other PUFA-derived metabolites that share the same enzymatic pathways as SPMs, will be established at baseline and post-intervention using mass spectrometry-based metabololipidomics. The concentration of all metabolites will be measured for plasma and peripheral blood mononuclear cells (PBMCs).

## **Overview of Study Phases**

Screening/Baseline: Subjects will be recruited in person at UNC Family Medicine Center at [name] in a private, closed-door room during a regularly scheduled office visit with [name]. We are using a convenience sample method, therefore everyone age 50-65 will be screened according to the criteria set forth for the study. During their visit, [name] will ask subjects if they wish to learn more about the study. If yes, the subjects will be directed to meet with the study coordinator. If the study coordinator is unavailable, [name] can complete the consent process during the office visit. Recruitment and informed consent will then follow the support documents provided, with either preoperative or post-operative consent and scripts being read by the study coordinator to the potential study subject. Upon full understanding and answering of any questions, the study coordinator will obtain written and verbal informed consent along with providing a copy of the consent form for the subject to keep themselves. We will recruit a total of 24 (n=12 men + 12 women) obese (BMI 30-40 kg/m^2) euglycemic and pre-diabetic subjects who will have similar distributions in their age (50-65 years), race, and smoking status. There will be no randomization for this study.

Intervention/Treatment: All 24 subjects will be administered 4 capsules of 'SPM Active' per day for 4 weeks +/- 2-4 days. There are 3 metabolites of the SPM family in the capsule, which are 17-HDHA (40mg) + 14-HDHA (80mg) + 18-HEPE (25mg). All three metabolites feed into pathways shown to improve insulin resistance and all three metabolites are decreased in obese subjects. The rationale for the dosing and time of intervention is based on the recommendations by the manufacture. The supplement will be provided by Metagenics. Note the manufacturer has not conducted bioavailability studies focused on the obese. Subjects will be instructed to consume 2 capsules with breakfast and 2 with dinner (4 total per day). Fasting blood will be drawn pre- and post-intervention using phlebotomy available under the direction of [name].

Baseline measurements will be taken prior to intervention so that each subject may serve as his/her own control. 12-hour fasting blood and serum will be drawn pre- and post-intervention for each subject by a licensed phlebotomist at the UNC Family Medicine Lab and under the direction of [name], the co-I. Each blood sample will be the size of 10 10mL plasma and serum tubes (9 plasma tubes + 1 serum tube) to ensure that enough B cells are collected from PBMCs for activations (see section 4.1 below). Therefore, a total of 10 tubes or ~100 ml of blood will be drawn twice during the study, 4 weeks apart. Finally, each subject will have his/her height (ft), body weight (lbs), blood pressure (mmHg), and pulse (bpm) taken at baseline and 4 weeks of intervention.

Follow up: Subjects will have two face-to-face visits and two phone contacts during the study. The first visit will be at baseline (pre-intervention) and the second visit will conclude the study (post-intervention). We will continuously monitor subject health status throughout the study via phone contact at the end of week 1 and week 3 following the start of supplementation. At the end of the study, all patients will follow up in a routine manner as designated by their physician at UNC Family Medicine.

Unscheduled Visits: If the study coordinator relays health concerns to [name] that will necessitate in-person visit.

